Effect of Individualized Repetitive Transcranial Magnetic Stimulation (rTMS) in Patients With Disorder of Consciousness

	Effect of Individualized Repetitive Transcranial Magnetic Stimulation (rTMS) in Patients With Disorder of Consciousness							
Application	Department of Rehabilitation, Zhujiang Hospital, Southern Medical University							
	Primary objectives: To examine whether individualized rTMS is more effective to improve CRS-R scores in DoC patients than the rTMS-sham control.							
	Secondary objective: (1)To examine whether individualized rTMS is more effective to improve relative spectral power of EEG in DoC patients than the rTMS-sham control;							
	(2)To examine whether individualized rTMS is more effective to improve functional connectivity of EEG in DoC patients than the rTMS-sham control;							
	(3)To evaluate the safety of rTMS in DoC patients.							
	rTMS applied on the Individual-targeted selection area will improve DOC patients' level of consciousness							
Design	Exploratory single-center, cross-over, double-blind, randomized controlled trial							
	This is a crossover pilot study. The CRS-R total score after two-stage treatments will be considered as the primary efficacy outcome, while high-density EEG analysis (relative spectral power and functional connectivity) will be the secondary outcome. In this context ^[1] , the sample size calculation will be based on an expected difference between the treatment groups of 20%, setting a significance level of 0.05% and a power of 80%. Considering patients' compliance and approximately 20% dropout rate during the study, the final sample size of 30 participants is needed. We consider this is an achievable sample size and adequate to allow for the dropout rate while still leaving a reasonable final sample.							
Eligibility	Inclusion Criteria:							
	1) acquired brain injuries less than 1 year and more than 28 days in DOC;							
	2) no medical history of neuropsychiatric diseases;							
	3) no contraindications for rTMS or EEG, no sedatives in use or other drugs that might interfere with brain stimulation, such as Na+ or Ca2+ channel blockers or NMDA receptor antagonists;							
-	4) stable state of disease and vital signs;							
	5) the families of the patients volunteered the patient to participate in the study and provided signed informed consent;							
	6) the integrity of the individualized stimulation target cortex are verified by MRI.Exclusion criteria:							
-	Exclusion Criteria:							

	1) patients in other non-invasive or invasive neuroregulation trials;							
	2) motor evoked potential (MEP) in M1 region cannot be induced by TMS pulse;							
	3) uncontrolled epilepsy, seizure within 4 weeks before enrollment;							
	4) metallic implant in the skull, pacemaker, craniotomy under the stimulated site, implanted brain device.							
Major interventions	10Hz rTMS							
Evaluating indicator	Primary outcome: The Coma Recovery Scale-Revised (CRS-R), a total of 23 points, is widely used to define the level of consciousness and assess neurobehavioral recovery of patients with DOC. It is based on six subscales that assess auditory (4 points), visual (5 points), motor (6 points), motor/speech (3 points), communication (2 points), and arousal processes (3 points). Each item of CRS-R is in good agreement with the diagnostic and differential diagnostic criteria of VS/UWS, MCS and EMCS. The higher scores mean a better outcome.							
	Secondary outcome: EEG will be acquired from 66 channels with positions of the International 10-20 System for 10 mins. The relative spectral power (RSP) and functional connectivity (FC) of participants will be calculated by the selected artifact-free EEG epochs at five frequency bands: δ (1-4 Hz), θ (4-8 Hz), α (8-13 Hz), β (13-30 Hz), and γ (30-45 Hz). The investigators will compute off-line analysis to calculate RSP and FC.							
Statistical method	Statistical hypothesis: Parametric hypothesis test							
	1. Group mean CRS-R scores before and after active/sham rTMS were analyzed by ANOVA with a two-stage crossover design;							
	2. The relative spectrum power and coherence before and after active/sham rTMS were analyzed by ANOVA with a two-stage crossover design;							
	3. If the overall means were unequal across each group, pairwise comparisons were performed using the SNK-q test;							
	4. Select the channel of interest at the average level of the active/sham rTMS group, extract the relative spectrum energies of each frequency band, and use the paired-sample t-test to compare the differences between the relative spectrum energies of the two groups;							
	5. Pairwise channel coherence was calculated along each channel at the mean frequency band of active/sham rTMS group using the paired sample t-test to compare the differences between the specific channel coherence of the two component pairs;							
	Non-parametric test was used if the normal distribution is not satisfied.							
	Effectiveness test: The efficiency test adopts the 2 test of paired R x C contingency table data. If the sample size is <40 or T <1, the Fisher exact probability method of four table data is used;							

#Table 1 Schematic timeline of the study

TIMEPOINT	Enrollment	Allocation	Post-allocation					Close-out
	- t ₁	t_0	t_1	t_2	t ₃	t 4	t ₅	t ₆
Enrolment	×							
Eligibility screen	×							
Informed consent	×							
Demographic information ¹⁾	×							
Medical history ²⁾	×							
Vital signs ³⁾	×			×		×		
Randomization		×						
Allocation		×						
Interventions								
Active rTMS			×		Washout	\rightarrow	×	
Sham rTMS			×		Washout	\rightarrow	×	
Assessments								
CRS-R ⁴⁾	×			×		×		×
EEG recording ⁵⁾	×			×		×		×
Adverse events			×	×	×	×	×	×

- 1) Demographic information includes the patients date of birth, sex and race;
- 2) Medical history includes DoC resulting from brain injury and other clinically significant past and present medical history;
- 3) Vital signs include blood pressure, pulse rate, respiration and body temperature;
- 4) CRS-R: Coma Recovery Scale-Revised;
- 5) EEG: Electroencephalogram.

Reference:

[1] Steven-A Julious. Sample size of 12 per group rule of thumb for a pilot study[J]. Pharmaceutical Statistics, 2005, 4(4): 287-291.

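### The primary CRS-R outcome is loosely worded, and the SNK-q step either repeats the F test or adds before-after tests that do not compare active with sham

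*Protocol*

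**What the plan says.** The trial is described as "Exploratory single-center, cross-over, double-blind, randomized controlled trial", and its primary objective is to examine whether "individualized rTMS is more effective to improve CRS-R scores in DoC patients than the rTMS-sham control".

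- **Design, primary outcome:** "The CRS-R total score after two-stage treatments will be considered as the primary efficacy outcome".
- **Design, sample size:** "the sample size calculation will be based on an expected difference between the treatment groups of 20" per cent, so the comparison in view is between treatments, not between sequences.
- **Statistical method, item 1:** "Group mean CRS-R scores before and after active/sham rTMS were analyzed by ANOVA with a two-stage crossover design".
- **Statistical method, item 3:** "If the overall means were unequal across each group, pairwise comparisons were performed using the SNK-q test".
- **Statistical method, item 4 (EEG):** a paired t-test is used to "compare the differences between the relative spectrum energies of the two groups", so only two groups are in view.
- **Table 1:** CRS-R is recorded at -t1, t2, t4 and t6, with stimulation at t1 and t5 and the washout between. Each stage therefore has a before score (-t1, t4) and an after score (t2, t6).
- **Inclusion criterion 1:** "acquired brain injuries less than 1 year and more than 28 days in DOC".

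**The concern.** The crossover ANOVA of item 1 implies an active-versus-sham term, and that term answers the primary objective. Two pieces of wording sit badly with it.

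First, taken literally, the primary outcome is a score recorded once both stages are complete. By then every patient has had both active and sham. Such a score can be compared only between the two sequences: between patients, on period 2 alone, and mixed with any carryover.

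Second, SNK-q is a procedure for sorting out three or more means. Here there are two treatments. The step has work to do only if the before and after scores of each arm are treated as four means, and some of the resulting pairs are then before-after changes within one arm. Patients enter between 28 days and 1 year after injury and may be improving in both periods whatever they receive. A significant gain under active beside a non-significant gain under sham could then be taken for efficacy, although it does not test the difference between them.

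**Working it through.** **Inputs.** From the Protocol: 30 patients, about 20% dropout, two treatments in two stages, CRS-R at -t1, t2, t4 and t6. The planned number reproduces as 2 × 12 = 24 (the 12-per-group rule in the title of the cited reference) and 24/(1 − 0.20) = 30. The Protocol gives no SD, correlation, recovery rate or allocation ratio. Assumed below: 24 completers, 12 per sequence, unit SD, two-sided 5% tests.

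**1. SNK-q with two means.** The criterion is q²/2 against F(1, df). At 22 df, q²/2 = 4.301 and F = 4.301. The decisions are identical, so the step is redundant.

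**2. SNK-q with four means.** There are 4 × 3/2 = 6 pairs: two before-after within an arm, one before-before, one after-after, and two that cross arm and time. None is the active-minus-sham difference in change.

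Simulation: no treatment effect; common gain g of 0.25, 0.30 or 0.40 SD; equal correlation of 0.6, 0.8 or 0.9 among the four scores; 10,000 runs per setting. Means at (-t1, t2, t4, t6) were (0, g, 0, g) if the gain is lost by t4, (0, g, g, 2g) if it is kept, and (0, g, 2g, 3g) if recovery continues through washout. A four-cell ANOVA with patient as block was followed by step-down SNK when F was significant. Rejection by the overall test at correlation 0.8:

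| Model and pattern | g = 0.25 | g = 0.30 | g = 0.40 |
|---|---|---|---|
| No period term, gain lost | 59% | 77% | 96% |
| No period term, gain kept | 53% | 70% | 91% |
| No period term, recovery continues | 37% | 47% | 67% |
| Period term, any pattern | 59% | 77% | 96% |

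Over all correlations, gains and patterns:

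- the overall test rejects in 22 to 100%;
- active significant and sham not occurs in 1 to 19%;
- the SNK pair active-after versus sham-after rejects in 0 to 5%;
- the period-adjusted active-minus-sham contrast rejects in 4 to 6%.

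**3. The literal t6 reading (illustration of an unlikely reading).** Let r be the between-period correlation. The two-period contrast of end-of-period scores has variance 2(1 − r)/24 on 22 df; 80% power needs a noncentrality of 2.93. At r = 0.8 the effect is 2.93 × √(0.4/24) = 0.378 SD (0.535 at r = 0.6, 0.268 at r = 0.9). Comparing sequences on unadjusted t6 scores has variance 2/12, so the noncentrality is 0.378/0.408 = 0.93 and power is 14% (24% at 0.6, 10% at 0.9). At r = 0.8, 80% power would need 111 per sequence; if half the period-1 effect persisted to t6, power would be 7%. With one baseline covariate correlated r with t6, variance 2(1 − r²)/12 × 21/20 on 21 df, power is about 33, 30 and 29% at r = 0.6, 0.8 and 0.9.

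**4. Ways of using the before scores, at r = 0.8 and effect 0.378 SD.** Let r₁ be the within-period correlation. Change scores: variance 4(1 − r₁)/24, 22 df. End-of-period scores adjusted for the baseline difference: variance 2(1 − r)[1 − ((r₁ − r)/(1 − r))²]/24 × 21/20, 21 df. End-of-period scores without adjustment have 80% throughout.

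| r₁ | Change | Baseline-adjusted |
|---|---|---|
| 0.80 | 51% | 78% |
| 0.85 | 63% | 80% |
| 0.90 | 80% | 88% |
| 0.95 | 98% | 98% |

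**The case against.** The strongest reply is that the plan, read as a whole, already compares active with sham. The term two-stage also appears in item 1, where it names the crossover. The objective, the design, the sample-size sentence and the CRS-R schedule all point to a score after each stage. This largely stands. A reader might infer that the trial will be judged on t6 alone and is therefore badly underpowered; no passage calls for a comparison of sequences at t6. The 24/14/10% powers also ignore the before scores that item 1 says are used.

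A second reply is that item 3 means the two groups, as item 4 does, so SNK-q is harmless, and that the Protocol nowhere states a four-mean analysis. That is fair: the four-mean reading is an inference from items 1 and 3 together, being the one under which the step does anything. Nor are rejections by the overall test false positives in the strict sense, since they detect a change that was put into the simulation. A reader might infer that the plan inflates the type I error for active versus sham. It does not: the after-after pair and the period-adjusted contrast stay at or near the nominal level or below it. The risk lies in reading within-arm results as efficacy, and no passage says that they will be read so.

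A third reply is that how the before scores enter the model may be left to the SAP, which is not at hand. Agreed; that silence is not held against the Protocol. What remains is an outcome whose stated timing does not match its analysis, and a stated step that does not serve the objective.

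**Conclusion.** The point holds as a cheap improvement, minor to moderate for an exploratory pilot. The timing of the primary outcome should be made explicit. The SNK-q step is redundant with two means; with four, its overall test and within-arm pairs respond to recovery shared by both arms. The sizes (22 to 100% for the overall test, 1 to 19% for active significant and sham not) rest on assumed gains of 0.25 to 0.40 SD, correlations of 0.6 to 0.9 and 24 completers split evenly. They show what could happen, not what is expected. Confidence is medium, because the Protocol does not say which means SNK-q is to compare.

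**What to change.** 1. State the primary outcome as the CRS-R total score at the end of each treatment period (t2 and t6).
2. Base the efficacy conclusion only on the period-adjusted active-minus-sham contrast from the two-period crossover model, with its 95% CI, adjusted for the between-period difference in the baselines already scheduled (-t1 and t4).
3. Delete SNK-q for CRS-R. Within-arm before-after changes may be reported descriptively.

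No visit or assessment is added. The covariate costs about one degree of freedom: at most about 2 points of power (80% to 78%) when within- and between-period correlations are equal, with a gain when the within-period correlation is clearly higher (80% to 88% at 0.90 against 0.80). Using t4 as a baseline relies on the washout, as the crossover comparison already does.

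### The sample-size paragraph prints a significance level of 0.05% and claims 80% power for a 20% difference with no scale and no SD, so 30 participants cannot be derived from it

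*Protocol*

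**What the plan says.** The Design row of the protocol calls the trial exploratory and a crossover pilot, and names the CRS-R total score as the primary efficacy outcome. It says the sample size will rest on "an expected difference between the treatment groups of 20%, setting a significance level of 0.05% and a power of 80" per cent. It then concludes: "approximately 20% dropout rate during the study, the final sample size of 30 participants is needed". The paragraph closes: "We consider this is an achievable sample size and adequate to allow for the dropout rate while still leaving a reasonable final sample".

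Three other places bear on this:

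- The Evaluating indicator row describes the primary outcome as "The Coma Recovery Scale-Revised (CRS-R), a total of 23 points".
- The Statistical method row gives the primary analysis: "Group mean CRS-R scores before and after active/sham rTMS were analyzed by ANOVA with a two-stage crossover design". It names no significance level.
- The sample-size sentence cites one source, reference [1], titled "Sample size of 12 per group rule of thumb for a pilot study".

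The protocol gives no SD, within-patient correlation, expected control mean, responder rate or sidedness.

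**The concern.** A power calculation for a mean score in a crossover needs four things: a level with its sidedness, a power, a difference in points, and the SD of the within-patient difference. The protocol gives the power. It gives the level in a form that is 100 times stricter than the usual 0.05, and the difference as a percentage of nothing named. It does not give the SD.

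The paragraph nevertheless says that these inputs lead to a need for 30 participants. Readers are told that a 20% effect would be detected with 80% power, and nothing in the document establishes that. A null result could not be described as having excluded such an effect on the strength of this statement. The only printed threshold is also one that the sponsor probably did not intend.

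**Working it through.** **Inputs from the protocol.** Level 0.05% (0.0005) as printed; power 80%; difference 20%, unscaled; dropout about 20%; N = 30; CRS-R maximum 23; two-period crossover. Completers: 30 × (1 − 0.20) = 24.

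**Reproducing 30.** It cannot be reproduced from the level, power and difference, because the scale and SD are missing. One route from the document's own content does give it exactly: 12 per group × 2 = 24, and 24 / 0.80 = 30. That route uses the title of the cited source and the dropout rate, and none of the three power inputs. The protocol does not say it was used, so this origin is an inference.

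**What 24 completers can detect.** Let d be the mean active–sham difference divided by the SD of the within-patient difference. With 12 patients per sequence, the crossover contrast follows a noncentral t with n − 2 = 22 degrees of freedom and noncentrality d√n. Solving for 80% power:

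| Level | Detectable d |
|---|---|
| two-sided 0.05 | 0.598 |
| one-sided 0.05 | 0.524 |
| two-sided 0.0005 (as printed) | 1.024 |

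At d = 0.60, power is 80.2% at two-sided 0.05 and 17.6% at two-sided 0.0005. The second figure applies only if the printed level is taken literally.

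**Reading 20% as relative to a mean score.** The means (6 to 12 points) and SDs of the within-patient difference (2 to 5 points) are assumptions, not protocol figures. With d = 0.20 × mean / SD, each cell shows the power of 24 completers at two-sided 0.05, then the enrolment needed for 80% power (completers / 0.80, rounded up):

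| Mean (20% of it) | SD 2 | SD 3 | SD 4 | SD 5 |
|---|---|---|---|---|
| 6 (1.2) | 80%; 30 | 47%; 65 | 29%; 113 | 20%; 174 |
| 8 (1.6) | 96%; 19 | 71%; 38 | 47%; 65 | 32%; 99 |
| 10 (2.0) | 99.7%; 14 | 88%; 25 | 65%; 43 | 47%; 65 |
| 12 (2.4) | ≈100%; 10 | 96%; 19 | 80%; 30 | 61%; 47 |

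Power reaches 80% in 7 of 16 cells. Enrolment runs from 10 to 174 and equals 30 in two cells. The largest SD that still gives 80% power is 0.20 × mean / 0.5984, which is 2.01, 2.67, 3.34 and 4.01 points for means of 6, 8, 10 and 12.

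**Reading 20% as a share of the scale.** 0.20 × 23 = 4.6 points. Then 80% power with 24 completers holds up to an SD of 4.6 / 0.5984 = 7.69 points. For assumed SDs of 2, 3, 4 and 5, power at two-sided 0.05 is about 100%, 100%, 100% and 99%.

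**Reading 20% as percentage points of responders.** A paired comparison (McNemar approximation, two-sided 0.05) needs at least 37 patients before dropout, so 30 is not reached.

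**The case against.** The strongest reply is that this is a small matter. The trial is labelled exploratory and a pilot, the 0.05% is plainly a slip, the figure appears only as a planning input, and the test level and sidedness may be set in an analysis plan that is not shown. No patient, visit or analysis would change.

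The reply continues that the 16-cell grid is the reviewer's choice. On the only scale the document itself supplies, the 23-point total, 30 participants are ample across the same SDs. Finally, a trial result is read from its estimate and confidence interval, not from a planning SD.

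Much of this stands:

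- The grid does not show that the trial is underpowered. It shows that the answer depends on figures the protocol does not give.
- The 4.6-point reading is as open as the relative one.
- The estimate and its interval remain interpretable whatever the planning paragraph says.
- The pilot-rule origin of 30 is no more than a strong numerical match, since some assumed SDs also lead to 30.

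It does not rescue the paragraph. A pilot need not claim 80% power, but this one does. Correcting the level alone leaves the 20% without a scale or an SD. A separate analysis plan would not alter a power statement already made in the protocol.

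**Conclusion.** The concern holds. The printed level is wrong by a factor of 100 if 0.05 was meant, and the claim of 80% power for a 20% difference has no basis in the document. The defect lies in the stated justification. It is not shown that 30 is too few.

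What can be said without outside figures is that 24 completers have 80% power for 0.60 SD of the within-patient difference at two-sided 0.05 (0.52 SD if one-sided). This assumes 20% dropout, equal sequences and the standard crossover contrast on 22 degrees of freedom. Any statement in CRS-R points needs an SD that the protocol does not supply.

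**What to change.** Correct the level to 0.05 (5%) and state whether it is one- or two-sided. Then take one of two routes.

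1. **Justify 30 as a pilot size and drop the claim of 80% power for 20%.** Possible text: *As this is a pilot, 30 participants will be randomised so that 24 complete both periods after 20% dropout (24 / 0.80). At two-sided 0.05, 24 completers give 80% power for a mean active–sham CRS-R difference of 0.60 SD of the within-patient difference.* The text should also say whether that difference is between post-treatment scores or between before–after changes. Without an SD it makes no claim in points.
2. **If the sponsor holds the figures,** state the 20% in CRS-R points and the SD of the within-patient difference with its source, and restate the power that 24 completers deliver.

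The second route tells the reader more. The first is honest if no SD is available. Either costs wording only: N stays at 30 and no patients are added. The restated power may be less favourable than the present claim.

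### Item 4 picks the EEG power channel at group-average level although the stimulated cortex is individualised, so an effect local to the stimulated site would be diluted

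*Protocol*

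**What the plan says.** The site of stimulation is specific to the patient. The Protocol's hypothesis is that "rTMS applied on the Individual-targeted selection area will improve DOC patients' level of consciousness", and inclusion criterion 6 requires that "the integrity of the individualized stimulation target cortex are verified by MRI". Each patient's target must therefore be known by the time eligibility is settled.

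EEG is the secondary outcome: "EEG will be acquired from 66 channels with positions of the International 10-20 System for 10 mins", with relative spectral power and functional connectivity computed in five frequency bands. Three items under Statistical method deal with it:

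- Item 2: "The relative spectrum power and coherence before and after active/sham rTMS were analyzed by ANOVA with a two-stage crossover design". No restriction to particular channels is stated.
- Item 4: "Select the channel of interest at the average level of the active/sham rTMS group", extract band power there, and "use the paired-sample t-test to compare the differences between the relative spectrum energies of the two groups".
- Item 5: "Pairwise channel coherence was calculated along each channel at the mean frequency band of active/sham rTMS group", again followed by a paired t-test.

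None of these items defines a channel, or a set of channels, by reference to the patient's own target.

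**The concern.** Item 4 states a selection rule, and that rule leaves out the feature that defines the treatment. If targets differ enough to fall under different electrodes, the channel chosen for the whole group lies over the stimulated cortex in some patients and away from it in others. A change in power confined to the stimulated area would then enter the comparison from only some of the patients. The rest would contribute noise and no signal.

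What is at stake is the item 4 evidence on secondary objective 1 (relative spectral power). A weak or null result there could reflect where the channel sits and not a lack of effect, and in an exploratory pilot such a result may shape the next study.

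**Working it through.** The Protocol has no power figure for EEG to reproduce, so this is a sensitivity calculation under stated assumptions.

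**Inputs from the Protocol**
- Planned sample 30 and dropout of about 20%, so completers = 30 × (1 − 0.20) = 24.
- Paired t-test of active against sham (item 4).

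**Assumptions, because the Protocol is silent**
- Test level: two-sided 5%.
- d: local effect, in SDs of the paired difference, at the channel over a patient's own target. It is set to 0.597 (0.60 rounded), the value that gives 80% power with 24 pairs.
- q: share of patients whose target lies under the common channel.
- The effect is purely local, i.e. zero at that channel in all other patients.
- The common channel is fixed and not picked from the observed differences.

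**Formulas**
- Mean paired difference at the common channel: q × d. The part lost is (1 − q) × d.
- SD of the paired difference: √(1 + d² × q × (1 − q)). The added term arises because some patients carry the effect and others do not.
- Standardised effect e = q × d / SD. Power comes from the non-central t distribution with 23 degrees of freedom, non-centrality e × √24 and critical value 2.069.

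**Worked case, q = 0.5:** mean = 0.5 × 0.597 = 0.2985; SD = √(1 + 0.3564 × 0.25) = 1.044; e = 0.286; non-centrality = 0.286 × 4.899 = 1.40; power = 27%.

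**Results, 24 completers, d = 0.597**

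| Share q with target at the common channel | Mean effect | SD | Standardised effect | Power |
|---|---|---|---|---|
| 1 (aligned, or all targets share the electrode) | 0.597 | 1.000 | 0.597 | 80% |
| 0.75 | 0.448 | 1.033 | 0.433 | 53% |
| 0.50 | 0.299 | 1.044 | 0.286 | 27% |
| 0.33 | 0.199 | 1.039 | 0.192 | 15% |
| 0.25 | 0.149 | 1.033 | 0.144 | 10% |

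**Checks**
- A simulation of 20,000 trials per setting (d = 0.6, 24 patients, targets allocated at random with probability q) gives 80%, 54%, 28%, 15% and 10%.
- With all 30 patients and d = 0.529, which again gives 80% at an aligned channel, the formula gives about 54%, 27%, 15% and 10%.
- For a larger local effect, d = 1.0 with 24 patients, the simulation gives over 99% at q = 1, then 90%, 55%, 29% and 18%. A strong effect tolerates moderate spread but not wide spread.

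If the effect is widespread, the common channel carries it in every patient. This is the q = 1 row, with no loss.

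**The case against.** The strongest reply is that the Protocol never predicts an EEG effect local to the coil. Its hypothesis concerns level of consciousness, and its EEG objectives concern spectral power and connectivity in general. For a widespread or network effect a common channel is a legitimate choice. This stands, and it is why the loss is conditional.

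The spread of targets is also unknown. Individualised may mean different regions, or different coordinates within one region served by the same electrodes. In the second case nothing is lost. This too stands.

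The power model is a simplification. It takes a fixed channel and a zero effect away from the target, whereas item 4 does not spell out how the group average leads to the choice. If the channel is picked by the size of the observed difference, the percentages do not describe that procedure. They show the mechanism and do not measure a defect in this trial.

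A reader might infer three stronger things, none of which the document supports:

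- *That the EEG effect is averaged away.* A local effect would be diluted, by an amount that depends on an unstated distribution of targets.
- *That item 5 has the same fault.* The word for average in item 5 qualifies the frequency band. No group-average choice of channels is stated there. What remains is only that its channel pairs are not referred to the patient's target.
- *That secondary objectives 1 and 2 could fail on channel alignment alone.* Item 2 covers both power and coherence without restriction to selected channels. It is not aligned to the target either, so it does not cure the mismatch, but the objectives do not rest on item 4 alone.

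It can also be said that electrode regions belong in a statistical analysis plan. That would answer a complaint about missing detail. Here the Protocol already states a selection rule, and the point concerns that rule.

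**Conclusion.** The point holds in a limited form. Item 4 fixes the channel for the power comparison at group level while the treatment is aimed at a patient-specific site, and no EEG analysis in the Protocol uses that site. Any effect on power local to the stimulated cortex is therefore diluted in proportion to the share of patients whose target is not under the selected channel.

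The cost in power runs from nothing (shared electrodes, or a widespread effect) to a fall from 80% to about 10% (a purely local effect with a quarter of targets at the common channel). The Protocol does not allow a choice within that range. The matter affects one secondary EEG analysis in an exploratory crossover pilot and does not touch the CRS-R comparison. It justifies adding an analysis, not replacing item 4.

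**What to change.** Keep the common-channel analysis of item 4 and add a target-aligned analysis beside it:

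1. For each patient, name the electrode or electrodes nearest the stimulated target. Fix the list before unblinding and use the same electrodes in the active and sham periods.
2. Compare relative band power at that set, active against sham, in the two-period crossover model of item 2.
3. Optionally, add coherence from that electrode set to the rest of the scalp in the same way.
4. Report the aligned and common-channel results together, so that a local and a widespread effect can be told apart.

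The 66-channel recordings are already planned and the target is already identified for inclusion criterion 6, so no new visits, recordings or patients are needed. The target must be recorded in a form that can be matched to electrodes, which the Protocol does not mention. The downside is small: one more exploratory EEG analysis, somewhat noisier than a whole-scalp mean if the effect turns out to be global.

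### Items 4 and 5 test the crossover EEG data with paired t-tests that have no period term, although item 2 plans a crossover ANOVA for the same measures

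*Protocol*

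**What the plan says.** The Protocol's Statistical method row gives two kinds of analysis for the EEG outcomes.

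- Item 2: "The relative spectrum power and coherence before and after active/sham rTMS were analyzed by ANOVA with a two-stage crossover design".
- Item 4, on relative power: "Select the channel of interest at the average level of the active/sham rTMS group", then extract each band and "use the paired-sample t-test to compare the differences between the relative spectrum energies of the two groups".
- Item 5, on coherence: "Pairwise channel coherence was calculated along each channel at the mean frequency band of active/sham rTMS group using the paired sample t-test".

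The fallback is general and names no test: "Non-parametric test was used if the normal distribution is not satisfied". The Evaluating indicator row states "EEG will be acquired from 66 channels". Under "Table 1 Schematic timeline of the study", EEG is recorded at enrolment, t2, t4 and t6, so each treatment period has its own recording before and after. The Design row allows for "approximately 20% dropout rate during the study, the final sample size of 30 participants is needed".

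**The concern.** In a two-period crossover, each patient's active-minus-sham difference carries the period effect with a sign that depends on the order of treatment. A crossover model estimates that effect and removes it. A paired t-test pools the differences over both orders and leaves it in.

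Two consequences follow if a period effect is present. The spread between the two sequences is counted as error, so the test is less sensitive. And if the sequences do not finish with equal numbers, the period effects no longer cancel in the mean difference. The channel-level results could then be less precise than item 2, or disagree with it on the same data. Patients enter between 28 days and one year after injury, so some drift in the EEG between periods is plausible.

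**Working it through.** **Inputs.** From the Protocol: 30 patients and about 20% dropout, so 30 × 0.8 = 24 completers. This agrees with the pilot rule of thumb in its reference list: 2 × 12 = 24, and 24/0.8 = 30. The Protocol gives no EEG standard deviation, effect size or period effect, and no figure of its own for this point. The following are therefore my assumptions: allocation 15:15, six dropouts at random, two-sided 0.05 (the Design row prints 0.05%, read here as 0.05), and a true effect τ = 0.6. All effects are in units of the SD of the within-patient difference. The period effect π raises the second period.

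**Model.** The active-minus-sham difference has mean τ − π in active-first patients (n₁) and τ + π in sham-first patients (n₂), with SD 1.

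- Paired t-test: averages all 24 differences, 23 df. Bias = π(n₂ − n₁)/24.
- Period-adjusted contrast: averages the two sequence means, 22 df. Standard error = (s/2)√(1/n₁ + 1/n₂), no bias.

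**Bias, given the split, at π = 0.5.** 13:11 gives 0.5 × (−2)/24 = −0.04 SD. 14:10 gives 0.5 × (−4)/24 = −0.08 SD. 15:9 gives 0.5 × (−6)/24 = −0.13 SD. The mirror splits have the opposite sign.

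**Chance of each split** (hypergeometric, C(15,n₁)·C(15,24−n₁)/C(30,24)) and simulated power at π = 0.5:

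| Active-first:sham-first | Chance | Paired power | Power with period term |
|---|---|---|---|
| 12:12 | 35% | 73% | 80% |
| 13:11 | 24% | 66% | 80% |
| 11:13 | 24% | 79% | 80% |
| 14:10 | 7.6% | 59% | 79% |
| 10:14 | 7.6% | 84% | 79% |
| 15:9 | 0.8% | 51% | 78% |

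9:15 also has a chance of 0.8%.

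**Average over splits at π = 0.5.** 0.349 × 73 + 0.241 × (66 + 79) + 0.076 × (59 + 84) = 25.5 + 34.9 + 10.9 = 71.3. The 15:9 split adds 0.008 × 51 = 0.4, and 9:15 adds at most 0.8. The average is about 72%.

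**Average power by size of period effect:**

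| π (SD) | Paired | With period term |
|---|---|---|
| 0.25 | 78% | about 80% |
| 0.5 | 72% | about 80% |
| 1.0 (extreme) | 50% | about 80% |

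**False positives.** With no true effect, average rejection by the paired test is about 3% at π = 0.5 and 1% at π = 1.0. The highest value at any split from 12:12 to 15:9 is 6%, at 15:9. The adjusted test stays at 5%.

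**Which outcome is compared.** Take four equally spaced EEGs.

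- Steady drift of 0.25 SD per interval gives levels 0, 0.25, 0.5, 0.75. Post-treatment values leave π = 0.75 − 0.25 = 0.5. Change scores leave (0.75 − 0.5) − (0.25 − 0) = 0, and nothing is lost.
- A rate that halves each interval gives levels 0, 0.5, 0.75, 0.875. Post-treatment values leave 0.875 − 0.5 = 0.375, and change scores leave 0.125 − 0.5 = −0.375. At 12:12 paired power is then about 76% against 80% either way.

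**The case against.** Item 2 does not itself name a period term, so the contrast with items 4 and 5 rests on the usual meaning of a two-stage crossover ANOVA. That is fair. Part of the point is a better choice of test, and the text does not contain an outright contradiction. But items 4 and 5 do name the paired t-test, so this is a stated choice and not detail left to an analysis plan.

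The size depends on a period effect that the documents do not give. Patients must be clinically stable, and if items 4 and 5 compare change scores, a steady drift over equal periods cancels. This stands: the loss may be nil, and at 0.25 SD it is about two points.

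A reader might infer more than the documents support, in three ways.

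- *That the paired test gives false positives or a systematic bias.* Under random dropout the two orders of each split are equally likely, so the bias averages to zero, and the test is on average conservative.
- *That the low power at an unfavourable split is typical.* The mirror split is just as likely and has higher paired power. The average is close to the 12:12 value.
- *That item 4 picks channels on the active-sham difference.* Its wording can equally mean a pooled average, which is harmless, or merely that group-averaged data are examined. It does not prescribe selection on the contrast.

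**Conclusion.** The point holds as a minor one. The Protocol plans a crossover model for spectral power and coherence, then names for channel-level tests of the same measures a method that ignores period. If a period effect survives in the outcome compared, the cost is mainly power: about 2 points at 0.25 SD and 8 points at 0.5 SD, on the assumptions stated above. Bias arises only given an unequal split and is small at the likely ones, about 0.04 SD at 13:11 or 11:13 for a 0.5 SD period effect.

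The channel-choice wording is a secondary clarification. Selection on the active-sham difference would be circular, and the text does not exclude it, but it does not call for it either.

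Item 2 and the primary CRS-R analysis are unaffected.

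**What to change.** In items 4 and 5, replace the paired t-test with wording such as:

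> For each channel (item 4) or channel pair (item 5), the active-minus-sham contrast is taken from the item 2 crossover model with patient, period and treatment. If normality fails, within-patient period differences are compared between sequences by a rank-sum test.

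As a clarification, add to item 4:

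> Channels are chosen without reference to the active-sham difference: listed before unblinding, or chosen from baseline data or data pooled over active and sham.

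The cost is wording and one error degree of freedom (23 to 22). With no period effect, power at 0.6 SD goes from about 80.4% to 80.2% at 12:12, and at worst from 80.5% to 77.8% at 15:9. Fixing channels in advance gives up a search for the strongest channel; choosing them from baseline or pooled data keeps a data-based choice that does not use the treatment difference.
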